3.6 Duration

If drain(s) cannot be removed after 21 days from the occurrence of POPF, the patient is enrolled and randomized if he or she fulfils the eligibility criteria, and then receives the assigned treatment. After undergoing the assigned treatment, patients are assessed daily for drain output and any complications. Drains are removed when the drainage amount is below 10 ml during 48 hours, and patients are discharged if they tolerate oral intake well and remain afebrile for 2 days after removal of all drains. After discharge, in-office visits were scheduled at week 1, 2, 4, 8, and 12. A follow-up CT is performed when there is clinical suspicion of POPF recurrence, or at 3 months after removal of the drain, whichever comes first. Therefore, the expected duration of subject participation is between 3 to 4 months.

3.7 Discontinuation

An individual patient's participation is discontinued if the patient decides to withdraw from the study, or the attending surgeon/physician-in-charge advises withdrawal from the trial based on medical reasons. According to intention-to-treat, the data of patients who withdraw from the study after being randomized are included for analysis.

4 Selection and Withdrawal of Subjects

4.1 Inclusion Criteria

Patients who undergo pancreatoduodenectomy (with or without pylorus preservation) and develop POPF that persists for 3 weeks after its occurrence.

4.2 Exclusion Criteria

- Patients are excluded if they are younger than 20 years of age, have active infection that is not adequately controlled [defined as body temperature $\geq 38.5^{\circ}\text{C}$ and/or leukocytosis (WBC count $>12,000$ /uL) or leukopenia (WBC count $<4,000$ /uL)], have current or history of severe heart, lung, kidney, or liver failure, have a Karnofsky Performance Score of <60 , are pregnant or lactating, or have received somatostatin or its analogue during the index admission, or decline to participate.

4.3 Subject Withdrawal

Patients can withdraw from the study after participating in the study. If a patient withdraws before being randomized, the patient is considered as being excluded because of decline to consent. If a patient withdraws after being randomized but before receiving the randomly assigned treatment, the assigned treatment is not given but the patient is included in the analysis according to the randomly assigned group (ITT). The type of treatment is

chosen according to the attending physician and his/her discussion with the patient. After withdrawal, patients are followed according to the follow-up scheme of this trial. The type and timing of the data to be collected for withdrawn subjects are the same as those who remain in the trial. No replacement for withdrawal is attempted.

4.4 Treatment of Subjects

Except the randomly assigned study/placebo intervention, patients are treated according to general surgical and clinical practice at the discretion of the attending physician.

4.5 Medication

Somatostatin or its analogue is not allowed throughout the trial period (during the index admission and follow-up period).

4.6 Monitoring for treatment effect

After receiving the assigned treatment, patients are assessed daily for fistula output and fistula- or treatment-related complications until the drain is removed. After drain removal, patients are assessed according to usual postsurgical inpatient care.

5 Assessment of Efficacy

5.1 Efficacy Parameters

- The primary efficacy end point is the days from the randomly allocated treatment to fistula closure. The date of fistula closure is defined as the date on which the drain is removed after an output of ≤ 10 mL during 48 hours, without recurrence of POPF within

the next 3 months.

- Secondary efficacy end points:
 - 30-day fistula closure rate: the proportion of patients in whom the drain can be removed by at day 30 after occurrence of POPF, without recurrence of POPF within the 3 months after removal of drain.
 - The rate of persistent or recurrent POPF after initial drain removal: fluid collection^a on follow-up CT, performed when recurrence of POPF is suspected clinically or at 3 months after removal of drain).
 - Length of hospital stay and hospital costs after the assigned treatment.
 - The rate of fistula-related complications: fever/infection^b, ileus^c, postpancreatectomy hemorrhage (PPH)^d after receiving the assigned treatment.

(a) Fluid collection: fluid accumulation on abdominal computed tomography with a diameter ≥ 4 cm.

(b) Fever/infection: body temperature $\geq 38.5^{\circ}\text{C}$, leukocytosis (WBC count $>12,000$ /uL) or leukopenia (WBC count $<4,000$ /uL). Fever/infection that is attributed to causes other than POPF is not considered as a fistula-related complication.

(c) Ileus: intolerance of oral or enteral feeding with distention of bowel on abdominal X-ray.

(d) Postpancreatectomy hemorrhage (PPH): all postoperative episodes of intraabdominal (blood in drainage fluid or hematoma on CT with dropped hemoglobin level) or gastrointestinal hemorrhage (blood in nasogastric tube, hematemesis, bloody or tarry stool), according to the International Study Group of Pancreatic Surgery (ISGPS) definition.³

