3.2 Study Design/Type

This trial is a prospective, superiority, parallel-group, randomized, double-blinded trial.

CONSORT 2010 Flow Diagram

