3.5 Trial Treatment

In patients randomized to receive standard care, only fistulography is performed to assess the condition of the fistula; occlusion is not performed. However, after fistulography, the drainage tube will be pulled outward for 2 cm in length and then fixed at skin again. Thereafter if patient remains asymptomatic, the drainage tube will be gradually withdrawn by 2 cm in length each day. The drainage tube will be removed when 48 hours drainage amount is less than 10 cc.

In patients randomized to undergo occlusion, the patient receives fistulography to assess the condition of the fistula, and then occlusion is performed using the following methods:

- In patients with a 7mm-calibered CW(closed wound) drain (perforated flat drain or round channel drain):

1. Use a Kelly or Mosquito forceps to clamp the tube of CWV drain.

[figure not shown]
2. Then an 18G puncture needle is inserted into the tube and remove the inner needle.

The small amount of diluted contrast medium can be slowly injected into the CWV tube. The tube and the route can be more clearly identified (fistulography).

3. A 0.035-inch guidewire can be inserted via the 18G puncture needle.

4. Remove the CW drain under the fluoroscopy. There may be some resistance initially when removing the CW drain. The proximal part of the removed CW drain is cut at 4 cm proximal to the previous skin fixation site (as shown in the following figure) and preserved in sterility for reinsertion.

5. A 40cm, 5Fr KMP catheter (Cook company) is inserted via the guidewire, and then the guidewire is removed.

6. Rinse the catheter hub and KMP catheter with 3ml 5% glucose water (Dextrose). Then the glue (33%, 1:2, 0.5ml of NBCA + 1ml Lipiodol) is slowly injected into the KMP catheter. Withdraw the catheter and continuously inject the glue until 5cm-long catheter remained inside the tract. The guidewire is inserted back through the catheter.

7. The planned reinserted portion of the original drain tube is inserted back into the drain tract via the guidewire. The guidewire is removed and the drain tube is fixed to the skin at previous fixation site.

8. Thereafter if patient remains asymptomatic, the drainage tube will be gradually withdrawn by 2 cm in length each day. The drainage tube will be removed when 48 hours drainage amount is less than 10 cc.

- In patients with a pigtail drainage of the post-operative fluid collection:

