5.2 Method and Timing

- Days from the assigned treatment to fistula closure: daily fistula output is assessed and recorded after fistulography with or without occlusion. Drains are removed when the drain output is ≤ 10 mL during 48 hours.
- 30-day fistula closure rate: the day on which POPF is diagnosed is day 1. The outcome is assessed at 3 months after initial removal of the drain. If recurrence is noted within 3 months after initial removal of the drain, the fistula is considered not healed by 30 days regardless of whether the drain could be removed by day 30 after the onset of POPF.
- The proportion of patients with persistent or recurrent POPF: a contrast-enhanced abdominal CT (non-enhanced CT is acceptable if contrast injection is contraindicated) is performed 3 months after removal of drains, or when there is suspicion of POPF recurrence, as suggested by the appearance of fever, ileus, or abdominal pain. Any intraabdominal fluid collection larger than 4 cm in its largest dimension is considered as evidence of POPF recurrence.
- Length of hospital stay and hospital costs after the assigned treatment: assessed at the date of discharge.
- The proportion of patients with fistula-related complications (fever/infection, ileus, bleeding/ postpancreatectomy hemorrhage (PPH) that develop after receiving the assigned treatment till 3 months after removal of drains. Patients are assessed daily for these complications during admission, and at week 1, 2, 4, 8, 12 after discharge at scheduled in-office visits.

6 Assessment of Safety

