6.3 Adverse Event Reporting

Any adverse event (AE) that occurs in randomized patients during the entire trial period should be carefully documented in the electronic case report form (eCRF) regardless of classification, seriousness, intensity, outcome, or causality.

Details of serious adverse events will be communicated by the local investigator to the local institutional review board (IRB).

The investigator should specify and report in the eCRF the nature of the sign or symptom, the date of onset, the date of resolution (duration), the intensity, the causality, interventions performed (if any), the relationship to trial treatment, and the outcome.

In the case of knowledge of an SAE, the investigator must immediately (within one working day of being notified of the event):

- Fill out at a minimum the following items of the internet-based SAE report: date of the AE, term of the AE, patient identification, name of reporter, treatment, result/outcome, assessment of both the seriousness and the relationship to the investigational treatment
- As soon as further information regarding the event is available (e.g. discharge note), the investigator should complete in the documentation in the eCRF and sign it electronically.
- Copies of the discharge note, of all the reports regarding examinations carried out and/or diagnostic findings should be sent to the lead investigator.

Periodic safety reports will be prepared by the lead investigator and forwarded to the IRBs of the participating sites.

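### Fever/infection drops out of the complication endpoint on an attribution call with no criteria or named assessor, and no all-cause analysis covers the window beyond 48 hours

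*Combined protocol and SAP*

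**What the plan says.** Section 5.1 lists fever/infection, ileus and postpancreatectomy hemorrhage as fistula-related complications. Fever/infection is met by a temperature of at least 38.5 °C, a white-cell count above 12,000/uL or one below 4,000/uL. The definition then adds an exclusion: "Fever/infection that is attributed to causes other than POPF is not considered as a fistula-related complication". Ileus and hemorrhage carry no such exclusion. Section 5.2 sets the window: complications count if they are ones "that develop after receiving the assigned treatment till 3 months after removal of drains".

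On blinding, section 3.2 calls the study a "prospective, superiority, parallel-group, randomized, double-blinded trial", and section 4.4 refers to a study/placebo intervention. Neither section says which roles are blinded or who attributes an infection.

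On the procedures, section 3.5 says that in standard care "only fistulography is performed to assess the condition of the fistula; occlusion is not performed"; the drain is then pulled out 2 cm and re-fixed. In the occlusion arm the drain is taken out: "The proximal part of the removed CW drain is cut at 4 cm proximal to the previous skin fixation site". Glue is injected, the kept portion is put back, and "The guidewire is removed and the drain tube is fixed to the skin at previous fixation site".

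Two other parts of the plan bear on the point. Sections 3.1 and 6.1 define a safety endpoint of fever/infection within 48 hours, using the same limits and no cause exclusion, and section 7.1 includes safety endpoints in the tests. Section 6.3 says: "Any adverse event (AE) that occurs in randomized patients during the entire trial period should be carefully documented", whatever the causality.

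**The concern.** The limits are objective, but the exclusion makes the endpoint depend on a causal judgement. If that judgement differs between arms, the comparison of complication rates is biased even when the true infection rates are equal.

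There are two routes to such a difference:

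- **Clues to the arm.** The drain is removed, cut and reinserted in one arm and only pulled out 2 cm in the other. Someone who infers the arm may attribute infections differently.
- **Procedure-related infection.** An infection caused by occlusion can literally be read as having a cause other than POPF, and so be dropped. Only the occlusion arm is exposed to removal, glue and reinsertion. This route does not need anyone to be unblinded.

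At stake is a claim that occlusion reduces fistula-related complications. That is a secondary endpoint, in a trial small enough for single calls to show in the rates.

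**Working it through.** **1. Denominators (section 7.2).** 51 / (1 − 0.10) = 56.7, rounded up to 57. At 2:1 this is 57 × 2/3 = 38 occlusion and 57 × 1/3 = 19 standard care, which matches the plan. All randomised patients are analysed.

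**2. Effect of one call.** The change in rate is 1/n: 1/38 = 2.6 points (occlusion) and 1/19 = 5.3 points (standard care).

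**3. Calls needed for significance from balance.** The documents give no expected complication rate, so the starting counts are assumed. The test is a two-sided Fisher exact test at 38 vs 19, removing events from one arm only until p < 0.05.

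| All-cause start (occlusion vs standard care) | Rate in each arm | Removed from occlusion only | Removed from standard care only |
|---|---|---|---|
| 6/38 vs 3/19 | 15.8% | 6 (p = 0.033) | not reachable |
| 8/38 vs 4/19 | 21.1% | 7 (p = 0.038) | 4 (p = 0.042) |
| 12/38 vs 6/19 | 31.6% | 9 (p = 0.048) | 5 (p = 0.042) |
| 18/38 vs 9/19 | 47.4% | 11 (p = 0.031) | 6 (p = 0.023) |

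The range is therefore about 4 to 11 calls, all in one direction. Removals in the occlusion arm favour occlusion and take 6 to 11; removals in standard care work against it and take 4 to 6. Three calls from balance leave a visible but non-significant gap: 12/38 vs 6/19 becomes 9/38 vs 6/19 (23.7% vs 31.6%, p = 0.54).

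**4. Calls needed when an imbalance already exists (assumed counts).**

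- 8/38 vs 8/19 (21.1% vs 42.1%): p = 0.12. Two occlusion-arm events removed gives 6/38 vs 8/19 (15.8% vs 42.1%): p = 0.049.
- 8/38 vs 6/19 (21.1% vs 31.6%): p = 0.52. Four removed gives 4/38 vs 6/19: p = 0.07. A fifth gives 3/38 vs 6/19: p = 0.048.

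**5. False-positive rate under differential attribution.** Take an equal all-cause rate r in both arms, with shares s1 (occlusion) and s2 (standard care) of events called POPF-related. The attributed counts are Binomial(38, r·s1) and Binomial(19, r·s2). Sum the probability of every pair of counts with Fisher p < 0.05. Both r (20% to 40%) and the shares are assumed.

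| Version | Share called POPF, occlusion / standard care | False-positive rate |
|---|---|---|
| All-cause | not used | 3.6–3.7% |
| Attributed | 70% / 70% | 3.3–3.6% |
| Attributed | 60% / 80% | 5.9–8.2% |
| Attributed | 50% / 80% | 8.9–14.5% |

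The attributed version does no harm when attribution is even. It exceeds 5% once the shares differ by 20 points.

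**6. What the plan already covers.** The first 48 hours have a tested fever/infection endpoint with no cause exclusion. After that, the remaining safety endpoint is any adverse event judged related to treatment, which is again an attribution. Adverse events are recorded throughout regardless of causality, but section 7.1 plans no all-cause fever/infection comparison from 48 hours to 3 months after drain removal.

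**The case against.** A reader might infer that attribution is made by ward staff who know the arm. The documents do not say so. They declare double blinding and describe the control as a placebo-type intervention. Both arms have fistulography, both leave with a drain fixed at the skin, and both follow the same withdrawal and removal rule. The operator must know the allocation, but nothing says the operator attributes infections. What stands is that the blinded roles and the assessor are undefined, so influence by arm is possible but not shown.

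A reader might also infer that the plan has no all-cause analysis at all. That is too broad, because the 48-hour safety endpoint is one. An infection blamed on the procedure in that period is counted there, and a later one is counted as a safety event if judged treatment-related. The gap is the rest of the window, in the complication comparison.

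Nor can a few calls turn balanced counts into a significant result. From 8/38 vs 4/19, four occlusion-arm calls give 4/38 vs 4/19, p = 0.42. A call also changes the combined complication rate only in a patient without ileus or hemorrhage.

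Finally, restricting a fistula-related endpoint to fistula-related events is a legitimate choice, and the all-cause version has weaknesses of its own. A low white-cell count alone qualifies, so leukopenia from chemotherapy would count. If faster closure led to earlier chemotherapy (an inference), that could shift the comparison against occlusion. Section 6.2 schedules a white-cell count only at 48 hours (or earlier with fever), so later detection is partly discretionary. This stands, and it is why the all-cause version should not replace the attributed one.

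**Conclusion.** The concern holds in a limited form. An objectively defined component is filtered by an unspecified causal judgement, and beyond 48 hours no planned analysis shows whether the result depends on that filter. One call is worth 2.6 or 5.3 points. Significance from balance takes about 4 to 11 one-way calls, but two can suffice where an imbalance exists. If attribution differs by 20 to 30 points between arms, the false-positive rate rises from under 4% to between 5.9% and 14.5%.

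These figures rest on assumed event counts, all-cause rates and attribution shares. They show how sensitive the endpoint is, not that bias will occur. The issue concerns one component of one secondary endpoint; time to fistula closure, the primary endpoint, is unaffected.

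**What to change.** Keep the POPF-attributed version as the main one and add to section 7.1, before any results are seen, wording such as:

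*As a sensitivity analysis, fever/infection meeting the temperature or white-cell limits from any cause will be compared between arms in all randomised patients, from the assigned treatment to 3 months after drain removal. It will be reported beside the POPF-attributed version. A reduction in complications will be claimed only if both versions point the same way.*

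Naming the person who attributes infections and stating whether that person is blinded would help the reader, but the fix does not depend on it.

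The cost is a short paragraph and one extra table. Adverse events are already recorded regardless of causality, so no new data collection or committee is needed. The downside is that unrelated events, such as leukopenia from chemotherapy, add noise and could dilute or shift the all-cause comparison. Reporting the two versions together lets the reader judge that.

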1.1 Investigational Treatment

Our experience has shown that trans-drain occlusion of the drain tract achieves fistula closure, enabling immediate removal of the drain. Trans-catheter occlusion requires the fluid collection to become walled-off, which usually takes 3 weeks. As the walled-off fluid collection can drain either via the percutaneous drain or via the pancreatic duct into the jejunum, occluding the point of entry of the drain tube into the fluid collection by gelfoam stops further fluid flowing through the drain tube. After occlusion, the secreted pancreatic juice can only drain through the pancreatic cut into the jejunum, and therefore the drain can

be removed right after embolization without recurrence of fluid collection along the tract of the drain.

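### Intra-abdominal haemorrhage can be recognised from drain fluid, a sign less available after occlusion, so the PPH component may be under-counted in the occlusion arm

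*Combined protocol and SAP*

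**What the plan says.** PPH is one of three components, with fever/infection and ileus, of the fistula-related complication rate, a secondary efficacy endpoint (sections 3.1 and 5.1). Section 5.1(d) counts "all postoperative episodes of intraabdominal (blood in drainage fluid or hematoma on CT with dropped hemoglobin level"), and separately counts gastrointestinal bleeding. Section 5.2 counts complications "that develop after receiving the assigned treatment till 3 months after removal of drains".

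Section 1.1 gives the purpose of occlusion: "occluding the point of entry of the drain tube into the fluid collection by gelfoam stops further fluid flowing through the drain tube". In section 3.5, the occlusion procedure removes the drain, injects glue along the tract and puts a cut length of tube back: "The planned reinserted portion of the original drain tube is inserted back into the drain tract via the guidewire". In standard care, "only fistulography is performed to assess the condition of the fistula; occlusion is not performed".

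Under section 4.6, "patients are assessed daily for fistula output and fistula- or treatment-related complications until the drain is removed". CT is specified at 3 months after drain removal, or earlier "when there is suspicion of POPF recurrence, as suggested by the appearance of fever, ileus, or abdominal pain" (section 5.2; section 3.6 is similar). The only blood test scheduled after treatment is a leukocyte count at 48 hours (section 6.2).

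Section 7.1 plans no analysis by the way a bleed was recognised.

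**The concern.** The two arms are compared on an event whose recognition depends partly on a device that the experimental procedure is meant to disconnect from the collection. The same bleed could show in a standard-care drain and not in an occlusion-arm drain. The difference is physical, so the blinding described in section 3 would not remove it. The direction favours occlusion.

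Safety is part of the trial objective (section 2), and bleeding behind a closed tract is a plausible harm of the procedure. A lower PPH count after occlusion could then reflect fewer bleeds or fewer bleeds seen, and the data as planned would not separate the two.

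**Working it through.** **Is the drain sign really less available after occlusion?**

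- For closed-wound drains, section 3.5 cuts the tube 4 cm proximal to the old skin fixation site (step 4). Glue is injected during catheter withdrawal until 5 cm of catheter remains in the tract (step 6). The cut piece is then reinserted and fixed at the same site (steps 7). It therefore lies superficial to the glue.
- For pigtail drains the tube is also cut at 4 cm, but no stopping length is given for the glue, so the same position is inferred.
- Section 1.1 names gelfoam and section 3.5 names NBCA glue. These passages must be reconciled. Both describe closing the tract, so the point does not turn on which applies.
- The standard-care tract is not occluded. The drain is pulled back 2 cm after fistulography and then 2 cm a day if the patient is asymptomatic, so its contact with the collection also declines.

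The drain sign is therefore less available after occlusion, as a matter of degree.

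**How large could the effect be?** The plan has no PPH figure to reproduce. Take equal true PPH risk in both arms. Let f be the share of PPH episodes recognised in standard care that show only in the drain, and l the fraction of those lost after occlusion.

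Observed risk ratio = 1 − f × l.

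Neither f nor l is in the documents, but f can be bounded. A drain-only episode must occur while the drain is in. If recognised bleeding is spread evenly over the window, f cannot exceed the share of the window with a drain in place. The window runs to 3 months after drain removal, taken as 90 days. Drain times are assumed exponential, and the medians are assumptions.

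| Assumed median control drain time | Mean = median / ln 2 | Drain share = mean / (mean + 90) | Lowest ratio (every bleed in that time drain-only, all lost) | Ratio if half are drain-only, all lost |
|---|---|---|---|---|
| 7 days | 10.1 | 10.1 / 100.1 = 10% | 0.90 | 0.95 |
| 14 days | 20.2 | 20.2 / 110.2 = 18% | 0.82 | 0.91 |
| 28 days | 40.4 | 40.4 / 130.4 = 31% | 0.69 | 0.85 |

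**In patients.** Section 7.2 plans 38 occlusion and 19 standard-care patients. At an assumed 10% true risk that is 38 × 0.10 = 3.8 and 19 × 0.10 = 1.9 bleeds. The most that would be missed in the occlusion arm is 3.8 × 0.10, 0.18 or 0.31, which is about 0.4, 0.7 or 1.2 episodes.

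**What the bound assumes.** It treats the standard-care count as complete, so that bleeds after drain removal are recognised by another route in both arms. If many such bleeds went unrecognised in both arms, the recognised ones would be concentrated in the drain period, and the ratio could fall below the bound. The same holds if bleeding itself clusters early.

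**The case against.** The strongest reply is that other routes remain open in both arms.

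- The fever, ileus and pain triggers in section 5.2 concern suspected fistula recurrence. They do not bar CT for suspected bleeding, and section 4.4 leaves other care to usual clinical practice.
- Patients are assessed daily for complications during admission, and then at weeks 1, 2, 4, 8 and 12 after discharge (section 5.2). Vital signs are taken every 8 hours as admission routine (section 6.2). Every patient is due a 3-month CT unless an earlier one is prompted.
- Gastrointestinal bleeding is recognised without the drain.
- Sections 6.3 and 6.4 require every adverse event to be recorded, including abnormal laboratory findings.

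All of this stands, and it narrows the problem. It does not equalise the endpoint. Blood in the drain is enough to meet 5.1(d), and a haemoglobin fall recorded as an adverse event does not by itself enter the PPH count.

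A reader might infer that the drain route is shut from day 0 in one arm and fully open in the other. The documents do not support this. Section 3.5 leaves a drain in after occlusion, section 5.2 records its daily output, and control drains are withdrawn stepwise too.

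A reader might also infer that a bleed known only from a haemoglobin fall can never count. Section 5.1(d) refers to a consensus definition that is not reproduced, so whether its parenthesis is exhaustive cannot be settled here. It is also unclear whether the haemoglobin condition applies to the drain sign. On either reading, that sign is less available after occlusion.

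**Conclusion.** The concern holds as a modest ascertainment difference in favour of occlusion. It affects one component of one secondary endpoint. A missed bleed changes the composite only in a patient with no other component, and the primary endpoint is untouched.

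The size cannot be derived from the documents. The range of 0.90 to 0.69 is a lower limit for the observed ratio under equal true risk, evenly spread recognised bleeding and the assumed drain times. It is not an estimate.

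A reader might infer that occlusion could appear to halve PPH, for example 5% against 10% with no true difference. That requires half of all episodes to be recognisable only through the drain and all of those to be lost. With drain coverage of 10% to 31% of follow-up, this could occur only if recognised bleeding were concentrated in the drain period, and nothing in the documents shows that it is. Nor do they support saying that a safety signal would go unrecorded, because recognised bleeds and haemoglobin falls are reportable as adverse events. What the plan lacks is a way to tell a difference in bleeding from a difference in detection. With 38 and 19 patients, one or two episodes can move the comparison.

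**What to change.** Keep the 5.1(d) definition for the main analysis, so that the trial stays with the consensus definition it cites. Then:

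1. Add an eCRF field recording how each PPH episode was recognised: drain fluid, CT with haemoglobin drop, gastrointestinal blood, or a combination.
2. Prespecify in section 7.1 a sensitivity comparison of PPH and of the composite that counts only episodes meeting criteria equally available in both arms: haematoma on CT with dropped haemoglobin, or gastrointestinal blood.
3. Tabulate by arm the episodes recognised only from drain fluid, and the bleeding or haemoglobin-fall adverse events that do not meet 5.1(d).

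The cost is one data field and a short addition to section 7.1. The sensitivity analysis will have fewer events and so less precision. It also cannot correct for CTs that were ordered because blood appeared in a drain, which is why the tabulation should be reported beside it. Patient care does not change.
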